## **PROTOCOL HISTORY**

Protocol		
Version Date Final		
4	16 June 2020	
3	18 December 2019	
2	29 July 2019	
1	31 May 2018	

### PROTOCOL AMENDMENT, VERSION 5: RATIONALE

Protocol GR40548 (Archway) has been amended to add "Device Dislocation" as an ocular Adverse Event of Special Interest (AESI).

Additional changes to the protocol, along with a rationale for each change, are summarized below:

- Administration schedule for self-administered antimicrobial and/or antiinflammatory ophthalmic drops before and after the Port Delivery System with ranibizumab (PDS) procedures have been updated (Section 5.1.1 and Appendix 17).
- Section 5.1.2 (Risks associated with intravitreal ranibizumab injection) has been updated per the latest Investigator Brochure.
- Device dislocation has been added to the list of anticipated risks associated with the PDS implant and/or implant insertion procedure (Section 5.1.3.7). In addition, language updates have been made to the other anticipated risks (vitreous hemorrhage, conjunctival bleb, conjunctival erosion, conjunctival retraction, rhegmatogenous retinal detachment, endophthalmitis) (Sections 5.1.3.1 to 5.1.3.6)
- Study treatment dose interruption criteria for local or systemic infection have been updated (Section 5.1.5.2, Table 2).
- The statistical method to evaluate the secondary efficacy objective "proportion of patients who undergo supplemental treatment" was modified in order to more accurately reflect the number of patients receiving supplemental treatment among those able to be assessed for the need for supplemental treatment (Section 6.4.2).
- Instructions on the management of device dislocation have been added (Section 5.1.5.8, Table 7) and recommended management of patients with vitreous hemorrhage, conjunctival retraction or conjunctival erosion, conjunctival bleb, endophthalmitis instructions have been updated (Sections 5.1.5.4 to 5.1.5.7).
- The names and contact information of the primary and secondary Medical Monitors have been updated (Section 5.4.1).
- Language has been added to clarify that adverse events associated with a special situation that also qualify as adverse events of special interest should be reported within 24 hours (Section 5.3.5.12).

- Language has been added to indicate that the Informed Consent Form instructs female patients to inform the investigator if they become pregnant (Section 5.4.3.1).
- The name of a Roche policy on data sharing has been corrected (Section 9.6).

Substantive new information appears in italics. This amendment represents cumulative changes to the original protocol.

#### **PROTOCOL SYNOPSIS**

TITLE:	A PHASE III, MULTICENTER, RANDOMIZED, VISUAL
	ASSESSOR-MASKED, ACTIVE-COMPARATOR STUDY OF THE
	EFFICACY, SAFETY, AND PHARMACOKINETICS OF THE PORT
	DELIVERY SYSTEM WITH RANIBIZUMAB IN PATIENTS WITH
	NEOVASCULAR AGE-RELATED MACULAR DEGENERATION
	(ARCHWAY)

PROTOCOL NUMBER:	GR40548
VERSION NUMBER:	5
EUDRACT NUMBER:	Not applicable
IND NUMBER:	113,552
NCT NUMBER:	NCT03677934
TEST PRODUCT:	Port Delivery System with ranibizumab
PHASE:	Phase III
INDICATION:	Neovascular age-related macular degeneration
SPONSOR:	F. Hoffmann-La Roche Ltd

#### **Objectives and Endpoints**

This study will evaluate the efficacy, safety, and pharmacokinetics of ranibizumab delivered via the Port Delivery System with ranibizumab (PDS) implant compared with ranibizumab 0.5 mg delivered as a monthly intravitreal injection in patients with neovascular age-related macular degeneration (nAMD). Specific objectives and corresponding endpoints for the study are outlined below.

Primary Efficacy Objective	Corresponding Endpoint

 
To evaluate the non-inferiority and equivalence in efficacy of ranibizumab delivered via the PDS Q24W with the 100-mg/mL formulation compared with that of 10-mg/mL (0.5-mg dose) Q4W intravitreal ranibizumab injections
 
	
 
Change from baseline in BCVA score at the average of Week 36 and Week 40, as assessed using the ETDRS visual acuity chart at a starting distance of 4 meters
 

	Secondary Efficacy Objectives	Corresponding Endpoints
• - 1	• To evaluate the relative efficacy of ranibizumab delivered via the PDS Q24W with the 100-mg/mL formulation compared with that of 10-mg/mL (0.5-mg dose) Q4W intravitreal ranibizumab injections, as assessed by visual acuity	
 
Change from baseline in BCVA score averaged over Week
 
60 and Week 64
 

١		
 
Change from baseline in BCVA score over time
 

۱ i		
 
Proportion of patients with BCVA score of 38 letters (20/200 approximate Snellen equivalent) or worse at the average over Week 36 and Week 40
 

		
 
Proportion of patients with BCVA score of 38 letters (20/200 approximate Snellen equivalent) or worse over time
 

		
 
Proportion of patients with BCVA score of 69 letters (20/40 approximate Snellen equivalent) or better at the average over Week 36 and Week 40
 

		
 
Proportion of patients with BCVA score of 69 letters (20/40 approximate Snellen equivalent) or better over time
 

		
 
Proportion of patients who lose < 10 or < 5 letters in BCVA score from baseline to the average over Week 36 and Week 40
 

		
 
Proportion of patients who lose < 10 or < 5 letters in BCVA score from baseline over time
 

		
 
Proportion of patients who gain ≥0 letters in BCVA score from baseline to the average over Week 36 and Week 40
 

		
 
Proportion of patients who gain ≥0 letters in BCVA score from baseline over time
 

• -	To evaluate the relative efficacy of	Change from baseline in CPT at Week 36
i a	ranibizumab delivered via the PDS Q24W with the 100-mg/mL formulation compared with that of 10-mg/mL (0.5-mg dose) Q4W intravitreal ranibizumab injections, as assessed by CPT on SD-OCT	
 
Change from baseline in CPT over time
 

י - ו ו	To evaluate the proportion of patients who undergo supplemental treatment with ntravitreal ranibizumab 0.5 mg	
 
Proportion of patients in the implant arm who undergo supplemental treatment with intravitreal ranibizumab
 
0.5 mg before the first, second, third, and fourth fixed refill- exchange intervals
 

		
 
Proportion of patients in the implant arm that undergo a supplemental treatment that requires subsequent additional supplemental treatments during the study
 

	Exploratory Efficacy Objectives	Corresponding Endpoints
• - t	Fo evaluate the impact of supplemental reatment with intravitreal ranibizumab ).5 mg	
 
Endpoints will be results-dependent based on number of supplemental treatment
 

	Exploratory Efficacy Objectives (cont.)	Corresponding Endpoints (cont.)
•	To evaluate the relative efficacy of ranibizumab delivered via the PDS Q24W with the 100-mg/mL formulation compared with that of 10-mg/mL (0.5-mg dose) Q4W intravitreal ranibizumab injections, as assessed by central subfield thickness on SD-OCT	
 
Change from baseline in CST at Week 36
 
Change from baseline in CST over time
 

•	To assess clinically relevant features using advanced analytics tools (including artificial intelligence-based tools) on multimodal images and clinical data	Clinically relevant features over time
•	To evaluate the development of macular atrophy in patients treated with the PDS Q24W with the 100-mg/mL formulation compared with those with 10-mg/mL (0.5- mg dose) Q4W intravitreal ranibizumab injections.	
 
Proportion of patients with macular atrophy at baseline, Weeks 36, 48, and 96
 
Change from baseline in macular atrophy area at Weeks 3 48 and 96
 

•	To evaluate the relative efficacy of ranibizumab delivered via the PDS Q24W with the 100-mg/mL formulation compared with that of 10-mg/mL (0.5-mg dose) Q4W intravitreal ranibizumab injections, as assessed by visual acuity	
 
Proportion of patients who gain ≥5 letters in BCVA score from baseline over time.
 

	Safety Objective	Corresponding Endpoints
•	To evaluate the safety and tolerability of ranibizumab, delivered via the PDS Q24W with the 100-mg/mL formulation compared with that of 10-mg/mL (0.5-mg dose) Q4W intravitreal ranibizumab injections	
 
Incidence and severity of ocular and systemic (non-ocular) AEs
 
Incidence, severity, and duration of AESIs, including PDS-associated AEs
 
Incidence, severity, and duration of ocular AESIs during th postoperative period (up to 37 days of initial implantation) and follow-up period (>37 days after implantation surgery)
 

	Pharmacokinetic Objective	Corresponding Endpoints
•	To characterize the serum pharmacokinetics of ranibizumab in patients after the initial fill and subsequent refill-exchanges in patients with the PDS	
 
Observed serum ranibizumab concentrations at specified timepoints
 
Additional estimated PK parameter values, including AUC0-6M, Cmax, Cmin, and t1/2 after PDS implant insertion
 

L	Exploratory Pharmacokinetic Objectives	Corresponding Endpoints
•	To evaluate potential relationships between drug exposure and the efficacy of the PDS	
 
Relationship between serum concentration or PK parameters for ranibizumab delivered via the PDS and efficacy endpoints
 

•	To characterize ranibizumab aqueous humor concentration over time	
 
Observed aqueous humor ranibizumab concentrations over time
 

Immunogenicity Objective	Corresponding Endpoint

 
To investigate the formation of serum anti- ranibizumab antibodies
 
	
 
The incidence of ADAs during the study, grouped in the following manner:
 
Patients who were ADA negative at baseline and became
 

	positive only after dosing
	
 
Patients who were ADA positive at randomization and ADA titer increased after dosing
 

	Patients who were ADA positive at randomization and ADA titer did not increase after dosing
Exploratory Biomarker Objectives	Corresponding Endpoints
• To explore relationships between aqueous humor free-VEGF concentrations over time and the efficacy of ranibizumab,	
 
Comparison of patients with and without aqueous humor free-VEGF present between refill-exchanges and needing supplemental treatment
 

delivered via the PDS Q24W with the 100-mg/mL formulation	
 
Comparison of patients with and without aqueous humor free-VEGF present between refill-exchanges and CST change from baseline over time
 

	
 
Comparison of patients with and without aqueous humor free-VEGF present between refill-exchanges and BCVA score change from baseline over time
 

 
To identify biomarkers that are prognostic of response to ranibizumab, are associated with acquired resistance to ranibizumab, are associated with susceptibility to developing adverse events (i.e., safety biomarkers), can provide evidence of ranibizumab activity (i.e., pharmacodynamic biomarkers), or can increase the knowledge and understanding of AMD-related disease biology
 
	
 
Relationship between biomarkers in blood and aqueous humor with disease characteristics and response to ranibizumab
 

	
 
Relationship between genetic variants (such as AMD risk alleles, polymorphisms within the complement pathway, and polymorphisms within the VEGF-A genetic locus) with the disease characteristics and/or response to treatment with ranibizumab
 

	
 
Relationship between imaging features with disease characteristics and/or response to treatment with ranibizumab
 

Exploratory Patient Experience Objectives	Corresponding Endpoints

 
To evaluate the preference of patients for ranibizumab delivered via the PDS for 40 weeks compared to intravitreal anti-VEGF treatment received in the 6 months prior to Day 1
 
	
 
Proportion of patients who report preferring ranibizumab treatment via the PDS compared with intravitreal anti- VEGF treatment, as assessed by the PPPQ, at Week 40 among patients in the implant arm
 

 
To evaluate patient-reported treatment satisfaction with ranibizumab delivered via the PDS for 40 weeks compared with that of Q4W intravitreal ranibizumab injections, as assessed by the MacTSQ
 
	MacTSQ total score at Week 40

ADA = anti-drug antibody; AE = adverse event; AESI = adverse event of special interest; AMD = age-related macular degeneration;  $AUC_{0-6M}$  = area under the concentration-time curve from 0 to 6 months; BCVA = best-corrected visual acuity;  $C_{max}$  = maximum serum concentration;  $C_{min}$  = minimum serum concentration; CPT = center point thickness; CST = central subfield thickness; ETDRS = Early Treatment Diabetic Retinopathy Study; MacTSQ = Macular Degeneration Treatment Satisfaction Questionnaire; PDS = Port Delivery System with ranibizumab; PK = pharmacokinetic; PPPQ = PDS Patient Preference Questionnaire; Q4W = every 4 weeks; Q24W = every 24 weeks; SD-OCT = spectral domain optical coherence tomography;  $t_{1/2}$  = half-life; VEGF = vascular endothelial growth factor.

#### Study Design

#### **Description of Study**

Study GR40548 (Archway) is a Phase III, randomized, multicenter, open-label (visual assessor [VA]–masked), active-comparator study designed to assess the efficacy, safety, and pharmacokinetics of 100 mg/mL ranibizumab every 24 weeks (Q24W) delivered via the PDS compared with ranibizumab intravitreal injections every 4 weeks (Q4W) at 0.5 mg (10 mg/mL) in patients with nAMD.

Patients will be randomly allocated in a 3:2 ratio so that approximately 216 patients will receive the PDS implant filled with 100 mg/mL ranibizumab Q24W (implant arm) and approximately 144 patients will receive monthly intravitreal injections of 10 mg/mL ranibizumab intravitreal injections Q4W (intravitreal arm).

Patients who are randomly allocated to the implant arm will have the implant (pre-filled with ranibizumab 100 mg/mL) surgically inserted on Day 1, which must occur 1–7 days (inclusive) after randomization (i.e., randomization and Day 1 visit assessments cannot be performed on the same day) and no later than 28 days from the last intravitreal ranibizumab 0.5 mg injection. If the implant insertion surgery (Day 1) cannot be completed within the visit window after randomization, the randomization visit assessments may be repeated and an additional intravitreal ranibizumab 0.5 mg injection may be required after discussion with the Sponsor. After Day 1, patients in the implant arm will have scheduled safety visit assessments on Days 2 and 7 ( $\pm$ 2 days) and will receive implant refill-exchanges with ranibizumab 100 mg/mL Q24W at Week 24 ( $\pm$ 7 days), Week 48 ( $\pm$ 7 days), and Week 72 ( $\pm$ 7 days).

Patients who are randomly allocated to the intravitreal arm will receive intravitreal ranibizumab 0.5 mg injections starting on Day 1, which is to be administered at the conclusion of the randomization visit (i.e., randomization and Day 1 visit assessments are performed on the same day). Patients will receive ranibizumab 0.5 mg, injected intravitreally Q4W ( $\pm$ 7 days) from Day 1 until Week 92.

In order to provide flexibility due to extenuating circumstances, it is possible that patients may receive additional study treatments until they are able to enroll into the long-term safety study.

Study visits will occur according to the schedule of activities relative to Day 1 (first study treatment). Study patients and all study site personnel with the exception of VA examiners will be unmasked to the study eye and study treatment assignment. To minimize bias, VA examiners will only conduct refraction and VA assessments and will be masked as best as possible to patient study eye assignment, study visit type, and patient treatment assignment.

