#### Table 2 Dosing Guidelines during Run-in Period and at Screening Visit

Anti-VEGF = anti-vascular endothelial growth factor.

a Randomization and the Day 1 visits should be completed within 21–28 days (inclusive) after last ranibizumab dose in the study eye.

All patients will return for a randomization visit and the Day 1 visit within 21–28 days (inclusive) after their last ranibizumab dose.

Patients who are randomly allocated to the implant arm will have the implant (pre-filled with ranibizumab 100 mg/mL) surgically inserted on Day 1, which must occur 1–7 days (inclusive) after randomization (i.e., randomization and Day 1 visit assessments cannot be performed on the same day) and no later than 28 days from the last intravitreal ranibizumab 0.5 mg injection. If the implant insertion surgery (Day 1) cannot be completed within the visit window after randomization, the randomization visit assessments may be repeated and an additional intravitreal ranibizumab 0.5 mg injection may be required after discussion with the Sponsor. After Day 1, patients in the implant arm will have scheduled safety visit assessments on Days 2 and 7 ( $\pm$ 2 days) and will receive implant refill-exchanges with ranibizumab 100 mg/mL Q24W at Week 24 ( $\pm$ 7 days), Week 48 ( $\pm$ 7 days), and Week 72 ( $\pm$ 7 days).

Patients who are randomly allocated to the intravitreal arm will receive intravitreal ranibizumab 0.5 mg injections starting on Day 1, which is to be administered at the conclusion of the randomization visit (i.e., randomization and Day 1 visit assessments are performed on the same day). Patients will receive ranibizumab 0.5 mg, injected intravitreally Q4W ( $\pm$ 7 days) from Day 1 until Week 92.

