#### 6.4.2 Secondary Efficacy Endpoints

The continuous secondary endpoints will be summarized using descriptive statistics based on all observed data. These continuous endpoints will also be analyzed following the same method as the analysis of the primary endpoint (see Section 6.4.1) with the independent variable, baseline BCVA score (continuous), in the model replaced with the baseline value of the corresponding endpoint (e.g., baseline CPT). The intercurrent events and data handling rules for the primary endpoint will apply here. Descriptive summaries will be provided for all secondary endpoints based on all observed data. Baseline is defined as the last available measurement prior to first treatment.

Unless otherwise specified, for binary secondary endpoints, the proportion of patients in each treatment group and the overall difference in proportions between treatment groups will be estimated using the weighted average of the observed proportions and the differences in observed proportions over the strata defined by randomization stratification factor of baseline BCVA (< 74 letters vs. ≥ 74 letters) using the Cochran-Mantel-Haenszel weights (Cochran 1954; Mantel and Haenszel 1959). All observed measurements will be included in the analysis regardless whether or not a patient has an intercurrent event. Confidence intervals of the proportion of patients in each treatment group and the overall difference in proportions between treatment groups will be calculated using the normal approximation to the weighted proportions (Mehrota and Railkar 2000). If the response rate is low, an unstratified analysis may also be performed.
The secondary efficacy endpoint, proportion of patients who undergo supplemental treatment, will be evaluated using only the patients who were able to be assessed for the need for supplemental treatment. The analysis will exclude any patients who discontinued treatment before the refill-exchange planned visit or who missed both refill-exchange visits, as these patients are not able to be assessed for the need for supplemental treatment. The unadjusted proportion of patients who undergo supplemental treatment as well as of patients who do not undergo supplemental treatment will be reported.

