-  Obtain from all study patients pre-treatment and prior to fluorescein angiography, if applicable. Hematology includes hemoglobin, hematocrit, quantitative platelet count, RBCs, WBCs, and differentials, including neutrophils, bands, lymphocytes, basophils, eosinophils, and monocytes (absolute and percent). Chemistry includes bicarbonate or total carbon dioxide (if considered standard of care for the region), sodium, potassium, chloride, glucose, BUN, creatinine, calcium, phosphorus, total and direct bilirubin, total protein, albumin, AST, ALT, lactic dehydrogenase, ALP, and uric acid. Urinalysis includes specific gravity, pH, blood, protein, ketones, glucose, bilirubin, urobilinogen, and microscopic examination (if any of the preceding urinalysis tests, other than glucose and ketones, are abnormal). Coagulation includes aPTT and PT.
- m Collect prior to implant refill-exchange and prior to fluorescein angiography (if applicable).
- n Perform IOP measurement prior to dilating eyes or procedure; the method used for a patient must remain consistent throughout the study for visits in the office. When performed at implant refill-exchange visit, IOP needs to be measured prior to implant refill-exchange.
- ° Should be performed in the surgical center using indentation tonometry (e.g. Tono-Pen) for the study eye only prior to the implant insertion surgery.
- p Upon completion of the implant insertion surgery, patients will have dilated indirect ophthalmoscopy performed to monitor the implant placement and to evaluate any potential implant problems (capturing the results of the indirect ophthalmoscopy findings on EDC is not needed at Day 1). Dilated ophthalmoscopy examinations will also be performed in the study eye at Day 2 and Day 7 (±2 days); afterward, perform dilated ophthalmoscopy examinations at each visit to monitor the implant placement and to evaluate other implant problems.
- q Historical OCT images taken around the time of diagnosis of nAMD (and before the start of anti-VEGF treatment) will be required to determine patient's eligibility at the screening visit. FAs if taken around the time of diagnosis of nAMD (and before the start of anti-VEGF treatment) must be submitted to the reading center as well and will be evaluated, but are not required to determine patient's eligibility. Refer to the reading center manuals for details.

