Continuous delivery of ranibizumab from the implant, with a prolonged fixed period between refill-exchange intervals, is a novel approach that may result in less-frequent need for treatment than monthly dosing and patient monitoring, while maintaining optimal visual outcomes. The Phases I and II PDS studies provided evidence of the safety and tolerability of the PDS and support the evaluation of the PDS in a Phase III study.

The purpose of this document is to provide details of the planned analyses for Study GR40548 (Archway). The analyses and endpoints specified in this document supersede the analysis plan described in the study protocol and the previous version of the Statistical Analysis Plan (SAP).

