#### 4.3 ANALYSIS OF TREATMENT GROUP COMPARABILITY

Demographic and baseline characteristics, such as age, sex, race, baseline disease characteristics (such as baseline center point thickness [CPT], and baseline BCVA), and number of prior anti-VEGF injections, will be summarized in the Efficacy Population by treatment group using descriptive statistics.

Baseline is defined as the last available measurement prior to first study treatment (PDS implant or post-randomization intravitreal injection).

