# 4.7.5 Ocular Assessments

Results of the following ocular assessments will be summarized by treatment group, by timepoint and by eye (study vs. non-study) as applicable, using descriptive summaries:

- intraocular pressure (IOP)
- slit lamp examination
- indirect ophthalmoscopy

Changes from baseline for IOP assessments will be tabulated. The presence of intraocular inflammation and vitreous hemorrhage, as determined on slit lamp examination, will be tabulated by grade (according to grading scales for flares and cells in Study GR40548 Protocol Appendix 7, and vitreous hemorrhage density and functional scales in Study GR40548 Protocol Appendix 8). The presence of retinal break or detachment as determined from ophthalmoscopy will be tabulated.

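### The baseline rule selects a surgical-center IOP for the implant arm only, and lets a delayed implant patient's repeat BCVA or OCT replace the randomization value

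*Protocol*

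**What the plan says.** SAP 4.3: "Baseline is defined as the last available measurement prior to first study treatment (PDS implant or post-randomization intravitreal injection". Protocol 6.4.2 has a shorter form: "Baseline is defined as the last available measurement prior to first treatment". SAP Section 1 gives the SAP precedence: "The analyses and endpoints specified in this document supersede the analysis plan described in the study protocol".

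In the intravitreal arm, randomization and Day 1 are one visit. In the implant arm, Day 1 is the surgery, 1–7 days after randomization, and the visit schedule runs "relative to Day 1 (first study treatment". If surgery misses its window, the Protocol (synopsis and 3.1) states that "the randomization visit assessments may be repeated and an additional intravitreal ranibizumab 0.5 mg injection may be required after discussion with the Sponsor". It does not give the order of the repeat and the injection, and neither document says which value is then baseline.

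For IOP, Protocol Appendix 1, Table 1 schedules a Day 1 measurement for every implant patient, with the footnote "Should be performed in the surgical center using indentation tonometry (e.g. Tono-Pen) for the study eye only", before insertion. The implant-arm footnotes and Protocol 4.5.5 require one consistent tonometry method only across office visits. The intravitreal arm's Year 1 and Year 2 footnotes require it throughout, without that limit. SAP 4.7.5: "Changes from baseline for IOP assessments will be tabulated".

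**The concern.** A rule that reads the same for both arms selects different measurements in each.

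- **IOP.** The implant arm's study-eye baseline comes from a different setting, and possibly a different method, from its own follow-up and from the other arm's baseline. Raised IOP is a listed risk in Protocol 5.1.2.1. A measurement artifact could therefore be read as a treatment effect, or hide one.
- **BCVA and OCT.** Only implant patients can have baseline replaced after assignment is known. Baseline BCVA enters the primary model twice, in the change score and as a covariate, while the stratum stays as recorded in IxRS at the original visit. The same model serves the primary tests at 4.5 letters and the EMA key secondary tests at 3.9 letters. Vision lost while waiting for surgery would be removed by a new baseline, which favors the implant. A gain after an extra injection would count against it.

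**Working it through.** **1. What the rule selects, from the schedules in Protocol Appendices 1 and 2**

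| | Implant arm | Intravitreal arm |
|---|---|---|
| Randomization to first study treatment | 1–7 days | same visit |
| IOP on Day 1 | yes: surgical center, indentation tonometry | no separate reading |
| BCVA or SD-OCT on Day 1 | not scheduled | no separate reading |
| Baseline IOP, study eye | Day 1 surgical center | randomization visit, office |
| Baseline BCVA/OCT, surgery on schedule | randomization visit | randomization visit |
| Baseline BCVA/OCT, window missed and assessments repeated | repeat value | cannot arise |

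The IOP asymmetry covers the whole implant arm. The BCVA/OCT asymmetry covers only delayed patients with a repeat.

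**2. IOP**

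Let m be the surgical-center reading minus the office reading. Change is the office follow-up minus baseline, so the implant arm's mean change moves by −m, with no covariate adjustment to soften it. An assumed |m| of 1–3 mmHg moves it by 1–3 mmHg. The documents give no value or sign for m.

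**3. The plan's power, as a reference point**

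Inputs from Protocol 6.1: SD 9.5, true difference −0.75, margin 4.5, 216 and 144 patients, 10% dropout and 10% for trimming.

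- Effective n: 216 × 0.9 × 0.9 = 175.0 and 144 × 0.9 × 0.9 = 116.6.
- SE = 9.5 × √(1/174.96 + 1/116.64) = 1.136.
- Noncentrality for non-inferiority = 3.75 / 1.136 = 3.30.
- One-sided 0.025 gives non-inferiority power of 90.9% and equivalence power of 90.5%. The stated figure of more than 90% is reproduced.
- At the 0.02485 level actually used, power is 90.8% and 90.4%.

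**4. BCVA shift**

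With change adjusted for baseline, the arm difference (implant minus intravitreal) moves by −β × f × δ. Here f is the share of implant patients with a repeat baseline, δ the mean of repeat minus original, and β the slope of follow-up on baseline (1 plus the slope of change on baseline). None of the three is in the documents; all are assumed.

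- Low end: β 0.6, f 3%, |δ| 3 gives 0.6 × 0.03 × 3 = 0.054 letters, which is 1.2% of 4.5 and 1.4% of 3.9.
- High end: β 0.8, f 15%, |δ| 5 gives 0.8 × 0.15 × 5 = 0.60 letters, which is 13% of 4.5 and 15% of 3.9.

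A large simulated ANCOVA with 5% of implant patients shifted by +3 moved the estimate from −0.0015 to −0.126, a change of −0.125. Its fitted β was 0.83, and 0.83 × 0.05 × 3 = 0.125.

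**5. Consequence for the 4.5-letter test** (β = 1, the largest effect; planned n; one-sided 0.02485)

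| f | Mean δ | Shift | Result |
|---|---|---|---|
| 5% | +3 | −0.15 | non-inferiority power 90.8% → 88.4% |
| 10% | +3 | −0.30 | non-inferiority power 90.8% → 85.7% |
| 5% | −3 | +0.15 | type I error at the margin 0.025 → 0.034 |
| 10% | −3 | +0.30 | type I error at the margin 0.025 → 0.045 |

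With 418 patients enrolled and the same losses, unshifted non-inferiority power is 94.4%.

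**The case against.** Much of the opposing case on BCVA stands.

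- **Few patients.** BCVA and SD-OCT are not scheduled on Day 1, so an implant patient treated on time has the same baseline visit as the other arm. A reader might infer that implant baselines are generally post-randomization, or that the primary result is tilted toward non-inferiority. The documents support neither: only a missed window with an optional repeat creates the problem, and delay and extra injection push in opposite directions.
- **The repeat has a purpose.** Protocol 3.1 says: "All patients will return for a randomization visit and the Day 1 visit within 21–28 days (inclusive) after their last ranibizumab dose". A repeat after an extra injection restores that interval, whereas the original value puts an unassigned injection between baseline and implant. A randomization anchor is thus a defensible alternative, not the correction of a plain error.
- **Selection is constrained.** The trigger is a missed window, not a score. VA examiners are masked as far as possible and do not see earlier scores. A stratum that disagrees with the covariate in a few patients does not in itself bias the model.
- **The extra injection is not study treatment.** A reader might take the parenthesis in SAP 4.3 to make that injection the first study treatment, giving the rule two meanings. Protocol 4.3.2.2 lists ranibizumab for delayed surgery separately from study treatment in the intravitreal arm, and the Protocol equates Day 1 with first study treatment. That largely settles it.
- **Timing.** SAP version 3 was written after the Primary and Update CSRs. Changing the main BCVA baseline now would be post hoc for Weeks 36/40.

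On IOP, it is fair that the tables are descriptive, that only the study eye is affected, and that no office tonometer is named, so a method difference is unproven. But the difference in setting is written into the schedule, and a comparable office reading exists for every patient who attended randomization as scheduled.

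**Conclusion.** The IOP point holds for the whole implant arm. Following SAP 4.3 exactly yields study-eye IOP changes that are not comparable between arms. The artifact equals whatever method or setting difference exists; 1–3 mmHg is an assumption. It touches descriptive safety tables and no hypothesis test.

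The BCVA/OCT point holds as a possibility only. The rule can give a post-randomization baseline in one arm, with bias in either direction, in a subset whose size is not reported and is probably small. The range of about 0.05–0.6 letters rests on assumed f, δ and β, and its top needs 15% of implant patients re-baselined with a 5-letter mean shift all in one direction. That is small against either margin, though even 0.15–0.30 letters would move error rates noticeably. It is enough to warrant a count and a sensitivity analysis, not a new primary definition. Sample size and alpha are unaffected.

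**What to change.** 1. In SAP 4.3 and 4.7.5, define baseline IOP in both arms as the last pre-treatment office reading, that is, the randomization visit. List the Day 1 surgical-center IOP separately. Where randomization assessments were repeated, state which visit is meant.
2. For BCVA, CPT and CST, report how many implant patients had repeated randomization assessments, and how many had an extra injection, before surgery.
3. Add a sensitivity analysis of the primary, EMA key secondary and post-Week 48 BCVA endpoints that uses, in both arms, the original randomization-visit score sent to IxRS. Keep the existing BCVA definition for the main analysis.
4. Do not substitute the screening value. Stratification already requires a randomization-visit BCVA, and in eligibility scenarios 1 to 4 ranibizumab is injected at the end of screening, so a screening baseline would precede an injection.

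The cost is SAP wording, one derived variable and one extra analysis; the schedules already collect the values. The small downside is that in delayed patients the sensitivity baseline lies further from the implant date.
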